*Secondary Endpoint: The percent reduction in wound area at Visit 5 relative to the size at randomization (Visit 2), per the imaging software assessments.*

The inclusion criteria limit the study to wounds which are difficult to heal, explaining why patients are not randomized if the wound area shrinks significantly between Visits 1 and 2. Therefore, greater reduction in wound size with pAF, than with SOC will suggest efficacy of pAF for wound treatment. To describe a trend in a statistical hypothesis testing framework, the following two-sided hypothesis will be assessed:

$$H_0: \mu_{\text{pAF}} = \mu_{\text{SOC}} \text{ versus } H_1: \mu_{\text{pAF}} \neq \mu_{\text{SOC}}$$

The secondary outcome variable will be the reduction in wound size at Visit 5 relative to the Visit 2 wound size (i.e.,  $100\% * (1 - \text{Visit 5 wound area} / \text{Visit 2 wound area})$ ), with all measurements expressed as the approximate area determined by the imaging software. Wound size should be measured at all study visits. To provide an intuitive effect size, percentage change from Visit 2 will be computed at visits 3, 4, and 5 (approximately 6, 12, and 25 weeks after randomization) with the changes at visits 3 and 4 considered as exploratory outcomes. If there are study visits outside of the visit's +/- 1 week window, all percentages will be divided by the number of elapsed days since Visit 2, so the outcome is expressed as a percentage change per day. If the change in wound size at Visit 5 follows a symmetric distribution a two-sample t-test will be performed, otherwise a Wilcoxon rank sum test will be used. As exploratory analyses, the prescribed analytic approach will be applied to the exploratory endpoints of percent reduction in wound area at Visit 3 and percent reduction in wound area at Visit 4.

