5.2 Methods for Withdrawals, Missing Data, and Outliers

The applicability of some measures will depend on whether or not the wound is (or has previously) closed. Values that are not observed because they are not applicable will be excluded from the pertinent analyses, rather than regarded as missing. Values that are not directly obtained but are implied by other measurements will use the implied value.

Multiple imputation (MI) will be applied for analyses of the secondary outcome. Using MI leverages partial information and attempts to reduce bias in final inferences that could result from a naive complete-case analysis. A minimum of ten data sets will be generated. Chained equations will be used along with variable selection; for imputing missing values for a given variable, the input variables will be limited to those that increase the R^2 value by at least 0.01. If feasible, MI will be conducted separately within each treatment arm. The pool of variables for the imputation process includes: wound area per the imaging software at Visits 1, 2, 3, 4, and 5; treatment arm if infeasible to impute by treatment arm; and indicators for comorbidities. The following comorbidities will be considered: diabetes, peripheral vascular disease, and immunosuppression. Imputation will exclude individuals

who were not randomized.

Visit measurements obtained outside the permissible window may or may not be used in the imputation model. We will determine the closest visit number to assign the out-of-window visit per the protocol's timing for follow-up visits. The out-of-window measurement will be used for the determined visit number in the case that the visit number does not already have a valid measurement (and if there are multiple out-of-window candidate measurements, the one closest to the protocol timing will be used). Otherwise, the out-of-window measurement will be ignored.

Multiple imputation may also be used for exploratory outcomes, as appropriate.

We do not plan to use different methods for missing data due to withdrawal compared with data missing for other reasons.

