5.3 Multiple Comparisons and Multiplicity

There is one primary endpoint (occurrence of post-randomization study-related SAEs on or before Visit 5), which is not intended to be tested between arms. Instead, descriptive summaries and confidence intervals will be constructed by study arm. There is one secondary endpoint (percent reduction in wound area at Visit 5 compared to Visit 2), which will be tested at $\alpha = 0.05$. The additional analyses are regarded as exploratory and therefore no adjustments are indicated for the multiplicity of testing; each will use $\alpha = 0.05$.

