7.3 Secondary Outcome Analysis

The secondary outcome is the percentage reduction in wound area at Visit 5 relative to wound area at Visit 2. Because reduction in wound area at Visits 3 and 4 are exploratory outcomes, the general definition for deriving percent reduction in wound area at Visit k relative to Visit 2 is

$$1 - \frac{\text{Visit } k \text{ wound area}}{\text{Visit 2 wound area}} \times 100\%,$$

with all measurements expressed as the area determined through the imaging software. Wound area will be reported in (cm^2), although for purposes of the percent reduction the units are immaterial. The percent reductions will be summarized overall and by assigned treatment arm for the ITT population, using means and standard deviations or medians and interquartile ranges, as appropriate given the observed skewness and presence of extreme outliers.

The inclusion criteria limit the study to wounds which are difficult to heal, explaining why patients are not randomized if the wound area shrinks significantly between Visits 1 and 2. Therefore, any greater reduction in wound size with pAF than with SOC will suggest efficacy of pAF for wound treatment. To describe a trend in a statistical hypothesis testing framework, the following two-sided hypothesis will be assessed:

$$H_0 : \mu_{pAF} = \mu_{SOC} \text{ versus } H_1 : \mu_{pAF} \neq \mu_{SOC}.$$

Note that μ_{pAF} (μ_{SOC}) represents the average percent reduction in wound area at Visit 5 compared to Visit 2 for the pAF (SOC) treatment.

To provide an intuitive effect size, percentage change from Visit 2 will be computed at Visits 3, 4, and 5 (approximately 6, 12, and 25 weeks after randomization). If there are study visits outside of the visit's ± 1 week window, all percentages will be divided by the number of elapsed days since Visit 2, so the outcome is expressed as a percentage change per day.

If the change in wound size at Visit 5 follows a reasonably symmetric distribution within each treatment arm, then a two-sided, two-sample, unpooled t-test will be performed to compare the mean percentage reductions at Visit 5 between arms for the ITT population. If the distribution is very asymmetrical in one or both arms, a Wilcoxon rank sum test will be used. In either case, Rubin's rules will be used to combine inferences across the multiply imputed data sets and the test will be declared statistically significant if the two-sided p-value is ≤ 0.05 .

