8 SAMPLE SIZE DETERMINATION

A sample size of $n = 30$ patients per group (total $n = 60$) is expected, though this may differ slightly because of the randomization procedure. Thirty participants in the pAF group with no study-related serious adverse events will provide a lower bound of the 95% one-sided exact binomial confidence interval for safety of 90% and provide enough evidence to move on to the next phase of study.

The power calculation depends on several assumptions:

- That 30 subjects are assigned to each treatment arm and that the secondary outcome is observed for all 60 subjects;
- That each subject has wound closure at Visit 5 (i.e., 100% wound area reduction relative to Visit 2) with probability $p_{SOC} = 0.2$ or $p_{pAF} = 0.5$ in the SOC and pAF arms, respectively; AND
- That for the remaining subjects in each arm, the wound area reduction percentage is uniformly distributed between 0% and 100%.

Using the Wilcoxon rank sum test (in this scenario, the response is very skewed in the pAF treatment arm), the Monte Carlo estimate of power is approximately 54%.

The trial has only modest power to detect statistically significant efficacy of pAF, but this is not unexpected for a phase I/II trial. More importantly, the sample size is sufficiently large to support the safety of moving on to the next phase of study if no study-related SAEs occur in the pAF arm, and the next phase of study would be appropriately powered for assessing efficacy.

pAF_in_Wounds_SAP_v_1_0

Final Audit Report

2021-03-11

Created: 2021-03-11
By: [name] ([contact])
Status: Signed
Transaction ID: CBJCHBCAABAAvUMP3dZCaNupqQJtavUadHtUrEKt9kc0

"pAF_in_Wounds_SAP_v_1_0" History

-  Document created by [name] ([contact])
2021-03-11 - 10:42:19 PM GMT- IP address: [name]
-  Document emailed to [name] MD ([contact]) for signature
2021-03-11 - 10:43:29 PM GMT
-  Email viewed by [name] MD ([contact])
2021-03-11 - 11:51:14 PM GMT- IP address: [name]
-  Document e-signed by [name] MD ([contact])
Signature Date: 2021-03-11 - 11:51:42 PM GMT - Time Source: server- IP address: [name]
-  Agreement completed.
2021-03-11 - 11:51:42 PM GMT

Adobe Sign

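### Does leaving the t-test or Wilcoxon choice for the secondary endpoint to an undefined symmetry judgement undermine the efficacy test?

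*SAP*

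**What the plan says.** SAP 7.3 gives two branches. The unpooled two-sample t-test applies "If the change in wound size at Visit 5 follows a reasonably symmetric distribution within each treatment arm". The other branch reads: "If the distribution is very asymmetrical in one or both arms, a Wilcoxon rank sum test will be used". The hypothesis is written in means, each of which "represents the average percent reduction in wound area at Visit 5 compared to Visit 2". For both branches, Rubin's "rules will be used to combine inferences across the multiply imputed data sets", and SAP 5.2 adds: "A minimum of ten data sets will be generated".

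Protocol section 8 (Statistical Method) words the rule differently: if the change "follows a symmetric distribution a two-sample t-test will be performed, otherwise a Wilcoxon rank sum test will be used".

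SAP 5.3 limits formal testing: "There is one secondary endpoint (percent reduction in wound area at Visit 5 compared to Visit 2"), tested at 0.05, with all further tests exploratory. SAP 7.4.1 repeats the symmetry rule for Visits 3 and 4, and 7.4.2 inherits it. SAP 8 bases its 54% power on one branch: "Using the Wilcoxon rank sum test (in this scenario, the response is very skewed in the pAF treatment arm").

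**The concern.** A test chosen from the final data without a written criterion leaves room for discretion in the trial's only non-exploratory hypothesis test. The trial is also open-label apart from the image assessor.

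Four details are missing:

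- Neither document names a symmetry statistic or a cut-off.
- The SAP's two phrases leave moderate skew without a test, whereas the protocol's wording covers every case.
- The SAP does not say whether symmetry is judged on observed or imputed data, or which rank-sum quantity Rubin's rules should pool.
- The hypothesis is about means, which the Wilcoxon test does not address in general.

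At stake would be a false-positive rate above 5%, power that depends on an unstated judgement, or a result open to challenge.

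**Working it through.** **Inputs.** From SAP 8: 30 per arm, all observed; closure (100% reduction) with probability 0.2 (SOC) or 0.5 (pAF); otherwise uniform on 0 to 100%. From SAP 5.3 and 7.3: two-sided 0.05 and an unpooled t-test. Skewness cut-offs and wound enlargement are assumptions, marked as such.

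**1. The SAP's 54%.** The probability that a pAF wound does better, counting ties as half, is 0.5×0.8 (pAF closed, SOC open) + ½×0.5×0.2 (both closed) + ½×0.5×0.8 (both open) = 0.40 + 0.05 + 0.20 = 0.65. With 30×(0.2+0.5) = 21 expected ties, the null variance is [61 − (21³−21)/(60×59)]/(12×30×30) = (61 − 2.61)/10,800 = 0.00541, so SE = 0.0735. Then 0.15/0.0735 = 2.04, and power ≈ Φ(2.04 − 1.96) = 53%. Simulation gives 54%, so the SAP's figure is right.

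**2. The t-test in the same scenario.** The means are 60 and 75. The variances, 10⁴×[p + (1−p)/3 − ((1+p)/2)²], are 1,066.7 and 1,041.7. SE = √[(1,066.7 + 1,041.7)/30] = 8.38; 15/8.38 = 1.79; power ≈ Φ(1.79 − 2.00) = 42%. Simulation also gives 42%. The two tests disagree on significance in 13% of trials.

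**3. What the SAP means by very skewed.** SAP 8 applies the phrase to its planned pAF distribution. On a 0-1 scale the third central moment is 0.625 − 3×0.75×0.6667 + 2×0.75³ = −0.03125. Divided by 0.10417^1.5 = 0.0336, this gives skewness −0.93. The same sum for SOC gives −0.008/0.0348 = −0.23. Cut-offs up to about 0.9 in absolute value therefore fit the SAP's usage.

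**4. Power of a mechanical rule in that scenario.** The rule is Wilcoxon if absolute skewness exceeds the cut-off in either arm. Ranges cover two skewness formulas.

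| Cut-off (assumed) | Trials sent to t-test | Power |
|---|---|---|
| 0.5 | 8-9% | 54% |
| 0.75 | 27-31% | 52-53% |
| 0.9 | 43-48% | 50-51% |

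The loss against Wilcoxon alone is at most about 4 points. Moving from 0.5 to 0.9 changes the conclusion in 3.8-4.6% of trials. Only cut-offs above the anchor cost more (1.0: 48-49%; 1.5: 42-43%).

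**5. Type I error.** With equal closure of 0.2, 0.35 or 0.5 in both arms, each fixed test and each mechanical rule rejects in about 5% of trials (4.8% to 5.2% across runs). If 15% of wounds enlarge in both arms (assumed), the rules reach at most 5.7%. Error of 5.7% to 6.7% would require claiming whichever p-value is smaller, which nothing in either document permits.

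**6. What naming Wilcoxon alone would do.** Power under assumed alternatives:

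| Scenario | Wilcoxon | t-test | 0.75 rule |
|---|---|---|---|
| SAP 8 | 54% | 42% | 52-53% |
| Closure 20% in both arms; 25% of SOC wounds grow by 0-100%, no pAF wounds grow | 26-27% | 50% | 45-46% |
| Closure 35% pAF, 20% SOC; 20% of SOC wounds grow, no pAF wounds grow | 48% | 63% | 54-55% |
| Closure as SAP 8; 10% grow in both arms | 46% | 24% | 45-46% |
| Closure as SAP 8; 20% grow in both arms | 38% | 17% | 38% |

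Neither test leads throughout. A shape-based choice stays close to the better one, or between the two.

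**7. Pooling.** An obvious way to fill the gap is to estimate the probability from step 1 with its tie-corrected standard error in each completed data set and pool both. With ten imputations, type I error was 4.7% to 4.9% with no missing data and 5.2% to 5.4% with 10% missing (assumed); power was 55% and 51%. That check used a within-arm bootstrap imputation in place of the SAP's chained equations.

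**The case for a change.** The best case for a change is that this is the only formally tested efficacy endpoint, and that moderate skew is not a rare corner. In the SAP 8 scenario the larger absolute sample skewness lies between 0.5 and 1.0 (an assumed band) in 46% of trials. The dual programming in SAP 5.6 verifies code, but two programmers cannot reproduce a judgement that nobody wrote down. With moderate skew, a reader could not tell from SAP 7.3 alone which test was prescribed. Closing the gap would cost only a few words.

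The documentation point stands: the criterion, the data set on which symmetry is judged, and the pooled rank-sum quantity are not written. The harm does not follow. Choosing by shape is not choosing by p-value, and step 5 shows that the error rate barely moves. The gap between the SAP's two phrases is one of wording. SAP 7.3 goes on to treat its two branches as covering every case when it applies Rubin's rules, and the protocol's version is exhaustive. Read together, anything not reasonably symmetric goes to Wilcoxon.

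The mismatch with a hypothesis about means is real on the Wilcoxon branch. But SAP 7.3 presents the test as a way to describe a trend, and a hypothesis about distributions would alter the sponsor's question.

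**Conclusion.** The observation is accurate but minor, and no change follows. Followed as written, with the protocol settling moderate skew, the plan gives a sound test. Type I error is about 5% (up to 5.7% with assumed enlargement in both arms). Power is within about 4 points of the stated 54% at cut-offs that match the SAP's own use of very skewed. Naming Wilcoxon alone would gain about 1 to 4 points over such a rule in the planning scenario. Against the 0.75 rule it would give up about 18 points if pAF works by preventing enlargement, a possibility the protocol allows for when it lists a 50% increase in wound size among its reasons to discontinue pAF. That is a trade-off, not a clear gain. The remaining gaps, in the symmetry statistic and the pooled quantity, are details that competent analysts can fill in a standard way.

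The setting also limits the stakes: SAP 8 concedes modest power and rests progression to the next phase on the absence of study-related SAEs in the pAF arm. The conclusion assumes that symmetry is judged from the shape of the data and not from the test results. The enlargement scenarios and cut-offs are assumptions, since the documents give none.

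### The secondary hypothesis is about mean percent reduction, but the skewed-data branch tests it with a Wilcoxon test, whose null is not equality of means

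*SAP*

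**What the plan says.** SAP 7.3 sets H0: mu_pAF = mu_SOC against a two-sided alternative, where mu "represents the average percent reduction in wound area at Visit 5 compared to Visit 2 for the pAF (SOC) treatment". The test then depends on the shape of the data:

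- If both arms look reasonably symmetric, "then a two-sided, two-sample, unpooled t-test will be performed to compare the mean percentage reductions at Visit 5 between arms for the ITT population".
- Otherwise: "If the distribution is very asymmetrical in one or both arms, a Wilcoxon rank sum test will be used".

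Whichever branch applies, results are combined over the imputed data sets and "the test will be declared statistically significant if the two-sided p-value is ≤ 0.05".

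Protocol section 8 (Statistical Method, secondary endpoint) states the same pair of hypotheses and the same switch: if the change "follows a symmetric distribution a two-sample t-test will be performed, otherwise a Wilcoxon rank sum test will be used".

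SAP section 8 calculates power for the rank branch: "Using the Wilcoxon rank sum test (in this scenario, the response is very skewed in the pAF treatment arm").

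Neither document restates the hypothesis for the rank branch, and neither assumes equal shapes or a pure shift, which would tie ranks to means. SAP 7.3 allows percent reduction to be summarised by medians and interquartile ranges when the data are skewed, so the plan does not guarantee that a mean difference is reported.

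**The concern.** The reference distribution of the rank sum test is built on the two arms having identical distributions. What the test responds to is theta = P(pAF > SOC) + 1/2 P(tie) moving away from 1/2. Theta = 1/2 and equal means are the same statement only under extra conditions, such as equal shapes. The switch is triggered when only one arm need be skewed, so the shapes may well differ. In the SAP's own planning scenario they do, with 20% v 50% of wounds at exactly 100% reduction.

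In that branch a p-value at or below 0.05 does not establish what the written hypothesis says. Percent reduction has an upper limit of 100% but no lower one, because wounds can enlarge. More closures on pAF could therefore sit beside poorer results in its open wounds, with an equal or lower mean. A report following the plan literally could then claim a difference in average reduction that the means do not show. This is the trial's one formal efficacy test at alpha 0.05 (SAP 5.3).

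**Working it through.** **Inputs from SAP section 8.** 30 per arm, no missing outcomes; closure probability 0.2 (SOC) and 0.5 (pAF); open wounds uniform on 0 to 100% in both arms. SAP 7.3 gives the two-sided 0.05 level.

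**Assumed input.** The documents give no other distribution for open wounds, so the pAF ranges below are assumptions. Enlargement is capped at 50%, borrowing the size of increase that protocol section 7 lists under discontinuation of study drug. That passage gives no frequency.

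**Formulas.** With closure probability p and open wounds uniform on (a, b):

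- mean = 100p + (1 - p)(a + b)/2
- theta = p_pAF × (0.5 p_SOC + (1 - p_SOC)) + (1 - p_pAF)(1 - p_SOC) × P(open pAF > open SOC)
- for SOC open wounds uniform on (0, 100) and pAF open wounds uniform on (a, b) with a ≤ 0 and b ≤ 100, P(open pAF > open SOC) = [b/(b - a)] × (b/200)

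**Step 1: the plan's own figure.**

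- SOC mean = 20 + 0.8 × 50 = 60; pAF mean = 50 + 0.5 × 50 = 75.
- theta = 0.5 × 0.9 + 0.4 × 0.5 = 0.65.
- Simulated Wilcoxon power (tie-corrected normal approximation, 100,000 trials) is 54.4% without and 54.1% with continuity correction. The stated 54% reproduces. The unpooled t-test has about 42% power here.
- Means and ranks point the same way in this scenario.

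**Step 2: no effect at all.** With identical distributions in both arms, Wilcoxon rejects in 4.9% to 5.2% of trials. It is valid for that null.

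**Step 3: equal means, different shapes.** pAF 50% closed, open wounds uniform on -50 to 90.

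- pAF mean = 50 + 0.5 × 20 = 60, equal to SOC.
- P(open pAF > open SOC) = (90/140) × 0.45 = 0.289; theta = 0.45 + 0.4 × 0.289 = 0.566.

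**Step 4: pAF mean slightly worse.** pAF 50% closed, open wounds uniform on -50 to 80.

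- pAF mean = 50 + 0.5 × 15 = 57.5.
- P(open pAF > open SOC) = (80/130) × 0.40 = 0.246; theta = 0.45 + 0.4 × 0.246 = 0.548.

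**Results, 30 per arm** (nominal rate in favour of pAF under a true null: 2.5%):

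| Scenario | Mean pAF v SOC | theta | Wilcoxon significant for pAF | Unpooled t significant for pAF |
|---|---|---|---|---|
| SAP section 8 | 75 v 60 | 0.65 | about 54% | about 42% |
| Equal means | 60 v 60 | 0.566 | 15.6% | about 3% |
| pAF mean lower | 57.5 v 60 | 0.548 | 11.0% | about 2% |

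In the equal-means case the unpooled t-test's total rejection rate stays near 5%. Median sample skewness in the pAF arm is -0.8 and -0.7 in the last two rows, against -0.9 in the scenario the SAP calls very skewed. The rank branch would plausibly be chosen in these cases too.

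**The case against.** The strongest reply is that nothing is wrong under the null that matters. Randomisation makes identical distributions the natural meaning of no effect, and there Wilcoxon holds its level. That stands. A reader might infer a general type I error failure, and the documents do not support it. Every elevated rate above needs pAF to act in two directions at once: more closures and poorer open wounds.

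Second, larger figures can be produced. With 60% closed on pAF and open wounds uniform on -100 to 100, Wilcoxon rejects in about 39% of trials at equal means. With 50% closed and open wounds uniform on -300 to 100, the pAF mean is 60 points worse and Wilcoxon rejects in only 7.5%. A reader might take these as the size of the problem. They need enlargement well beyond 50% (in the second case up to four times the Visit 2 area), and nothing in the documents supports that. The only open-wound distribution given is uniform on 0 to 100% in both arms.

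Third, it is tempting to conclude that Wilcoxon must be replaced. Brunner-Munzel hardly alters the rejections:

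- Equal means, 50% closed, open wounds -60 to 100: 15.8% v 18.7% for Wilcoxon.
- Equal means, 60% closed, open wounds -100 to 100: 33.5% v 39.1%.
- pAF mean 10 points worse (50% closed, open wounds -100 to 100): 9.6% v 11.9% significant in favour of pAF.

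The wording of the hypothesis does most of the work, not the choice of rank test.

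Fourth, this is a secondary endpoint in a phase I/II trial, framed as describing a trend. Closure is tested separately by Fisher's exact test (SAP 7.4.3), so an opposing pattern might be noticed. This limits the consequence. It does not restate the hypothesis or guarantee that the mean difference is shown.

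**Conclusion.** The mismatch is real and is visible in the text. The hypothesis is on means, the branch used in the planning scenario tests something else, and nothing bridges the two. It is a fault in what a significant result is allowed to conclude. It is not a loss of error control when pAF has no effect.

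With enlargement capped at 50%, Wilcoxon favours pAF in 15.6% of trials at equal means and in 11.0% when the pAF mean is 2.5 points lower. These rates rest on assumed open-wound ranges, a 50% closure rate on pAF, complete data and 30 per arm. They show that the gap can matter. They do not predict that it will. The plan should be amended because the correction is nearly free and changes the conclusion that a significant rank result can carry.

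**What to change.** In SAP 7.3 and protocol section 8:

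1. Give the rank branch its own hypothesis, H0: P(pAF > SOC) + 1/2 P(tie) = 1/2, and report that estimate with its confidence interval.
2. State that significance in this branch means a pAF wound tends to do better (or worse) than an SOC wound, not that mean reductions differ.
3. Always report the unpooled mean difference with its 95% CI beside it, and base any statement about average percent reduction on that result only.

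Optionally, replace Wilcoxon with Brunner-Munzel. Its null is the restated one, it allows ties and unequal shapes, and it gives an estimate and standard error that can be pooled by Rubin's rules. Power in the SAP section 8 scenario stays at about 54% to 55%. It does not by itself remove rejections at equal means, so items 1 to 3 are needed either way.

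The cost is wording and a few lines of code, with no extra patients or data. The downside is that a significant rank result will support a narrower statement than one about average reduction.
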